# PLEASE EMAIL COMPLETED FORM TO BIG TEN CRC ADMINISTRATIVE HEADQUARTERS

# **SYNOPSIS**

TITLE	Phase Ib study of the safety and efficacy of Gemtuzumab Ozogamicin (GO) and Venetoclax in patients with relapsed or refractory CD33+ acute myeloid leukemia					
PHASE	Ib					
OBJECTIVES	Primary Objective: To assess the maximum tolerated dose of Venetoclax when administered with Gemtuzumab Ozogamicin (GO) in patients with AML.					
	Secondary Objectives: To assess the efficacy of this combination in achieving overall response rate (ORR) and anti-leukemic activity; characterize any adverse effects of GO in combination with Venetoclax; and estimate the relapse-free, event-free and overall survival.					
	Exploratory Objectives: To assess the effects of therapy on quality of life; assess genomic minimal residual disease (MRD) to determine the kinetics of response and association with relapse-free survival.					
STUDY DESIGN	Dose-escalation study (Cohorts 1-3) to determine whether there is a dose- limiting toxicity.					
KEY ELIGIBILITY CRITERIA	Eligible patients, 18–75 yrs, will have relapsed/refractory AML, as defined by the World Health Organization classification; ECOG Performance score 0-2; adequate organ function; and do not meet exclusion criteria including WBC >25 × 10  /L (hydroxyurea permitted to decrease WBC count), unresolved ≥grade 2 clinically significant nonhematologic toxicities from prior anticancer therapy or unresolved ≥grade 2 DIC, other active malignancy within 1 year before study entry, major organ dysfunction, active infections, or pregnancy or breastfeeding.					
STATISTICAL CONSIDERATIONS	Standard 3+3 design					
TOTAL NUMBER OF SUBJECTS	N = 15-24 (n = 9-18, plus 6).					
ESTIMATED ENROLLMENT PERIOD	18 months					
ESTIMATED STUDY DURATION	30 months					

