# **1.2** Investigational Treatment

# 1.2.1 Gemtuzumab Ozogamicin (GO)

GO consists of a humanized anti-CD33 monoclonal antibody linked to calicheamicin, a potent antitumor enediyne antibiotic. GO binds to CD33, an antigen expressed on the surface of more than 90% of AML blast cells. Binding of GO is followed by internalization and intracellular release of calicheamicin, leading to DNA damage and subsequent mitochondria-dependent apoptosis.

The original FDA approval for GO was based on phase II studies of 9 mg/m2 given on days 1 and 14 in 277 patients with AML in first relapse, where it showed good tolerability, an overall response rate (ORR = complete remission (CR) and complete response with incomplete platelet recovery (CRp)) of 26%, and a median relapse-free survival (RFS) of approximately 6 months in patients aged >60 yrs (review). To reduce the hematological and hepatic toxicities seen with this dose and schedule, a French Cooperative group performed a phase II trial of GO 3 mg/m^2 given on days 1, 4, and 7, in patients with relapsed AML (n = 57). The rationale for lower dosing was based on responses observed with doses of 1–4 mg/m2 in the initial phase 1 study of GO. The administration of fractionated doses of GO was derived from observations of rapid re-expression of CD33 on the cell surface after an initial exposure (review). The ORR was 33%, and median survival improved to 11 months, with a marked reduction in adverse effects (e.g., median duration of >grade 2 thrombocytopenia fell to 21 days).

In a randomized phase III Cooperative group trial this GO dosing and schedule was next combined with a standard AML chemotherapy regimen ("7+3") and compared to "7+3" alone—resulting in significant gains in 2 year event-free survival (EFS), overall survival (OS) and RFS, despite no difference in initial CR rates. These benefits were confirmed in a recent meta-analysis as extending to 6 years in AML patients with low or intermediate risk cytogenetics, suggesting addition of GO increases the eradication of LSC, particularly in more "mature" AML with CD33-expressing LSC (reviews).

Note that patients in CR or CRp after induction received two further consolidation cycles of Gemtuzumab Ozogamicin (3 mg/m^2 on day 1) according to their initial randomization, in combination with daunorubicin and cytarabine.

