# 2.1.3 Exploratory Objectives

- Longitudinal assessment of genomic minimal residual disease (MRD) to determine the kinetics of response and the association with relapse-free survival.
- Explore the impact of CD33 variants, and the degree of CD33 expression on leukemic blasts, on the response rates and relapse-free survival.
- Explore the relationship between leukemic blast BH3 profiling and response rates.

• Explore the relationship between leukemic blast expression of anti-apoptosis proteins (BCL-2, BCL-XL and MCL-1) and response rates.

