#### 9.2 Definitions of Survival Endpoints for AML

Overall Survival	All evaluable patients entered into trial; measured from the date of entry to the date of death from any cause; patients not known to have died at last follow- up are censored on the date they were last known to be alive				
Relapse-free Survival	Only patients achieving CR or CRi; measured from the date of achievement of a remission until the date of relapse or death from any cause; patients not known to have relapsed or died at last follow-up are censored on the date they were last examined				
Event-free Survival	All patients entered into trial; measured from the date of entry to the date of treatment failure, disease relapse, or death from any cause; patients not known to have any of these events are censored on the date they were last examined				
Adapted from European LeukemiaNet. 					

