# 12.6.2 Analysis Plans for Secondary Objectives

Descriptive characteristics of all adverse effects of GO in combination with Venetoclax (using CTCAE v5 criteria) will be reported; and the efficacy of the combination in achieving ORR (includes CR/CRi) and anti-leukemic activity (includes CR/CRi/PR), as defined by the revised IWG criteria), RFS, EFS, and OS in subjects. The effects of therapy on quality of life, fatigue, and physical function at D0 (trial entry) and the end of every other month for 1 year (see section 8.1) will be reported and analyzed using generalized linear modeling.

All time-to-event outcomes (e.g. survival) will be calculated using Kaplan Meier methods and exploratory log-rank tests will be used to compare treatment effect between groups based on genomic MRD, CD33 DNA polymorphisms, BH3 profiling and anti-apoptosis protein levels in PB MBCs at presentation and after 1 week of Venetoclax.

*Sample size permitting:* Hazard ratios (HR) and 95% CIs will be produced. Time-to-event outcomes with a competing or semi-competing risk (e.g. CIR) will be analyzed using cumulative incidence curves and exploratory comparisons between arms will be made using Grey's test. Rate ratios and 95% CIs will be presented. Chi squared tests will be used to assess the treatment effect between cohorts for all categorical variables and t-tests or Mann Whitney tests will be applied for continuous measures as appropriate.

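### Section 12.6.2 plans marker log-rank tests whatever the sample size; for relapse-free survival in a handful of responders, the usual chi-squared p-value can mislead, so a permutation p-value should be specified

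*Combined protocol and SAP*

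**What the plan says.** Section 12.6.2 opens its survival paragraph with "All time-to-event outcomes (e.g. survival) will be calculated using Kaplan Meier methods", and continues that "exploratory log-rank tests will be used to compare treatment effect between groups based on genomic MRD, CD33 DNA polymorphisms", BH3 profiling and anti-apoptosis protein levels. The wording is a commitment, and nothing in the sentence depends on sample size. The condition appears at the start of the next paragraph: "Sample size permitting:* Hazard ratios (HR) and 95% CIs will be produced". It governs the hazard ratios and the items after them (cumulative incidence with Gray's test, rate ratios, chi-squared, t and Mann-Whitney tests).

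RFS is one of the outcomes covered. Section 9.2 restricts it: "Only patients achieving CR or CRi; measured from the date of achievement of a remission". Section 2.1.3 names it as a marker outcome twice: for MRD, to "determine the kinetics of response and the association with relapse-free survival", and for CD33, to "Explore the impact of CD33 variants, and the degree of CD33 expression on leukemic blasts, on the response rates and relapse-free survival".

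The synopsis gives the trial size as "N = 15-24 (n = 9-18, plus 6"; section 12.3 gives 18-24 from the same components. The plan states no target response rate, no significance level for the log-rank tests, no choice between a chi-squared and an exact p-value, and no minimum group size or number of events.

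**The concern.** The ordinary log-rank p-value refers the statistic to a chi-squared distribution with one degree of freedom, which is a large-sample approximation. With two to four patients in a group, the statistic takes only a few possible values and the approximation can be poor. The author of 12.6.2 evidently had small numbers in mind, since the hazard ratios and later tests carry a condition, but as placed it misses the log-rank tests.

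At stake is how the marker results read. A reader shown p = 0.02 from two patients against four cannot tell that a permutation test on those six patients could not give less than 0.067.

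**Working it through.** **Inputs.** Trial size: 9 + 6 = 15 and 18 + 6 = 24, which reproduces the synopsis range (the lower limit of 18 in section 12.3 is not 9 + 6). Response rates, used as assumptions: 33% for fractionated GO in relapsed AML (section 1.2.1: "The ORR was 33%, and median survival improved to 11 months"); 26% for GO at the originally approved dose (same section); and 19% CR for venetoclax alone in relapsed/refractory disease (section 1.2.2). A 50% rate is added to cover a better result for the combination. Two-sided 0.05 is assumed, in line with the 95% intervals in 12.6.2.

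**Responders = rate × N.**

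| Rate | N = 15 | N = 18 | N = 24 |
|---|---|---|---|
| 19% | 2.9 | 3.4 | 4.6 |
| 26% | 3.9 | 4.7 | 6.2 |
| 33% | 5.0 | 5.9 | 7.9 |
| 50% | 7.5 | 9.0 | 12.0 |

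So about 3-8 at the cited rates, and 8-12 at 50%.

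**True size.** With no marker effect and no censoring, each of the C(n, k) ways of placing k group-1 patients in the order of relapse is equally likely. The true size is the share of these placements in which the chi-squared p-value is at or below 0.05. The permutation p-value is the share with a statistic at least as large as the one observed, so its minimum cannot be below 1/C(n, k).

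**One case by hand, 2v4.** Both group-1 patients relapse first. Observed minus expected = 2 − (2/6 + 1/5) = 1.467. Variance = (2/6)(4/6) + (1/5)(4/5) = 0.382. Chi-squared = 1.467² / 0.382 = 5.63, p = 0.018. There are C(6, 2) = 15 placements and none is more extreme, so the permutation p is 1/15 = 0.067. Two of the 15 placements give chi-squared p ≤ 0.05, so the size is 2/15 = 13.3%.

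**All splits at n = 5-8.** The first four result columns are full enumeration without censoring; the last two are simulated sizes (40,000 replicates, exponential times).

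| Split | Placements at p ≤ 0.05 | True size | Smallest chi-squared p | Smallest permutation p | Size, 40% random censoring | Size, 40% administrative censoring |
|---|---|---|---|---|---|---|
| 1v4 | 1/5 | 20.0% | 0.046 | 0.200 | 12.2% | 19.8% |
| 2v3 | 1/10 | 10.0% | 0.039 | 0.100 | 3.7% | 9.0% |
| 1v5 | 1/6 | 16.7% | 0.025 | 0.167 | 13.9% | 16.5% |
| 2v4 | 2/15 | 13.3% | 0.018 | 0.067 | 7.1% | 10.1% |
| 3v3 | 2/20 | 10.0% | 0.025 | 0.100 | 5.4% | 8.2% |
| 1v6 | 1/7 | 14.3% | 0.014 | 0.143 | 13.2% | 14.5% |
| 2v5 | 2/21 | 9.5% | 0.008 | 0.048 | 7.0% | 6.7% |
| 3v4 | 3/35 | 8.6% | 0.010 | 0.029 | 6.3% | 6.5% |
| 1v7 | 1/8 | 12.5% | 0.008 | 0.125 | 12.1% | 12.7% |
| 2v6 | 3/28 | 10.7% | 0.004 | 0.036 | 7.4% | 8.0% |
| 3v5 | 5/56 | 8.9% | 0.004 | 0.018 | 6.8% | 6.7% |
| 4v4 | 4/70 | 5.7% | 0.007 | 0.029 | 6.4% | 6.0% |

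With four uncensored responders the chi-squared version cannot reach 0.05 either, so the problem starts at five.

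**Whole-trial OS and EFS (n = 15-24).** Near-even splits have a size of about 6-7%; splits with one or two patients in a group have about 9-17%.

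**The case against.** The strongest reply is that the plan promises little. It labels the tests exploratory, sets no significance level and ties no decision to them. A permutation log-rank test is still a log-rank test, so the chi-squared version at 5% is an assumption. That stands, and every size above is conditional on it. It does not remove the point, because an unqualified log-rank test is ordinarily the chi-squared version, and which one is meant should be stated.

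Three further limits also stand. An even 4v4 split is close to nominal. Random censoring mostly lowers the size, and censoring is plausible: patients may leave for transplant (section 5.6), and progression follow-up after stopping treatment lasts six months (section 7.2). And the number of responders rests on single-agent rates, whereas the trial expects synergy. At 50% there would be 8-12 responders, with uncensored sizes of about 7-8% for near-even splits at n = 10-12.

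A reader might infer that every marker p-value among 5-8 responders is about twice too liberal and beyond the reach of any exact test. The table does not support that: at n = 7-8 with at least two patients per group, a permutation test can reach 0.05. Nor do the documents make all marker conclusions depend on these tests. Section 2.1.3 ties BH3 profiling and anti-apoptotic proteins to response rates, and section 8.1.1 also relates the rate and depth of MRD reduction to RFS and OS.

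**Conclusion.** The point holds as a minor one about exploratory reporting. The log-rank tests lie outside the sample-size condition, and RFS will probably be compared in very few patients. If the chi-squared p-value at two-sided 0.05 is used, its uncensored size with at least two patients per group ranges from 6% (4v4) to 13% (2v4). At 40% censoring it is roughly 4-8% if censoring is random and 6-10% if administrative. Single-patient groups stay at 12% or more throughout. With 5-6 responders, or one patient in a group at n = 5-8, the smallest permutation p is 0.067-0.20, so any chi-squared result below 0.05 there comes from the approximation alone.

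Two stronger readings are not supported. The primary endpoint (DLT) and the MTD decision do not use these tests. And although several markers and outcomes are tested, the chance of at least one false lead was not established here; multiplicity would produce false leads even with tests of exact size.

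**What to change.** In section 12.6.2, state that log-rank p-values for marker comparisons of RFS, and of any other time-to-event outcome where a marker group is very small, are exact permutation p-values. State also that where the smallest attainable permutation p exceeds 0.05, only Kaplan-Meier curves and numbers at risk are shown. The plan should put a number on very small; groups of one or two are where whole-trial inflation is greatest. OS and EFS comparisons with near-even groups can keep the standard test.

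Moving the log-rank sentence under the existing sample-size condition would be simpler, but it leaves open what size is enough and which p-value is used.

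The cost is a sentence or two and a few lines of code, with no change to data collection or sample size. Permutation p-values are somewhat conservative (true size about 0.02-0.05 where rejection is possible), they assume that censoring does not depend on the marker, and the smallest comparisons become descriptive. The change does not address multiplicity across markers and outcomes.

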# 5.1 Dose Escalation Rules

- Three to six subjects will initially be enrolled at dose level 1. If none of the 3 subjects experience a dose limiting toxicity (DLT) during the first cycle of therapy, an additional three subjects will be enrolled at dose level 2. If none of the 3 subjects at dose level 2 experience a dose limiting toxicity (DLT), an additional three subjects will be enrolled at dose level 3. If all subjects in dose level 3 complete the first cycle of therapy without DLT, 3 more subjects will be enrolled into dose level 3 to ensure only 0-1 of 6 subjects have a DLT. There will be no further escalation beyond dose level 3.
- Alternatively, if 1 of the first 3 subjects within any given dose cohort experiences a DLT, an additional 3 subjects will be enrolled at that dose level. If only 1 of the total 6 subjects in a dose level experience a DLT, the study will proceed to the next dose level as planned. If 2 of the total 6 subjects in any given dose cohort experience a DLT, the next lower dose level will be explored and considered the maximum tolerated dose (MTD) if no more than 1 of 6 subjects experience a DLT. If this occurs in cohort 1, the dose will be decreased to cohort -1 and if 2 or more DLTs are reached in dose level -1, the study will be put on hold and a protocol amendment will be considered. [see Section 6.4 for "Stopping Rules"]
- The MTD for Venetoclax in combination with Gemtuzumab Ozogamicin is defined as the dose level at which fewer than 33% of subjects experience a dose limiting toxicity (DLT), and specifically is the dose level at which less than 2 out of 6 subjects experience DLT. That dose will be the recommended Phase II dose (RP2D).
- Once the RP2D has been identified, we will expand this cohort to include an additional six patients to further evaluate the efficacy and safety profile of the RP2D.

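### Chi-squared tests between dose cohorts of 3 to 12 patients rest on an approximation that cannot hold at these sizes; exact intervals, or exact tests, should replace them

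*Combined protocol and SAP*

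**What the plan says.** Section 12.6.2 (Analysis Plans for Secondary Objectives) specifies: "Chi squared tests will be used to assess the treatment effect between cohorts for all categorical variables and t-tests or Mann Whitney tests". The part on continuous data reads in full: "t-tests or Mann Whitney tests will be applied for continuous measures as appropriate". The paragraph opens with the condition "Sample size permitting", without a threshold or a fallback. For competing-risk outcomes it adds that "exploratory comparisons between arms will be made using Grey's test", although Sections 5 and 12.1 describe a single-arm study. No exact test, k-sample test for continuous data, continuity correction or significance level is named.

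The cohort sizes come from Section 5.1. "Three to six subjects will initially be enrolled at dose level 1"; if no dose-limiting toxicity is seen, "an additional three subjects will be enrolled at dose level 2", and dose level 3 follows in the same way. Once the recommended phase 2 dose is known, "we will expand this cohort to include an additional six patients". The dose-cohort table lists 200, 400 and 600 mg, with 100 mg as a fallback level.

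Elsewhere, Section 12.6.1 only presents dose-limiting toxicities by dose. Sections 12.6.2 and 12.6.3 describe adverse events in tables. Section 12.6.3 models quality of life, fatigue and physical function, including their relation to dose.

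**The concern.** The chi-squared reference distribution is a large-sample approximation, usually relied on only when expected counts reach about 5. No unexpanded cohort here can come near that for a binary outcome. The test is nevertheless prescribed for every categorical variable, which includes overall response and anti-leukemic activity, the efficacy results that will be read next to the recommended dose.

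A report that follows the sentence literally could call a difference significant on the strength of one event in three patients, or could reach the opposite conclusion because the software applied a correction by default. The plan does not settle which p-value would be reported.

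For continuous measures the issue is different. The two named tests each take two groups. With three or four doses they either do not fit or imply a set of pairwise tests that the plan neither lists nor adjusts for.

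**Working it through.** **Inputs.** Cohort sizes are from Section 5.1. Two-sided 5% is an assumption, in line with the 95% intervals in Section 12.6.2, because no level is stated. A 33% response rate is the figure quoted in Section 1.2.1 for fractionated gemtuzumab; 10% is an illustrative low event rate.

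**Plan's own figure.** Three cohorts of 3 to 6 plus 6 gives 3×3 + 6 = 15 and 3×6 + 6 = 24, the synopsis total of 15–24. The dose declared the MTD has 6 patients, and expansion makes 6 + 6 = 12. Cohorts therefore range from 3 to 12.

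**Expected counts.** With common event rate r, a cohort of n has expected counts nr and n(1−r), which sum to n. The smaller is at most n/2: 1.5 for n = 3 and 3 for n = 6.

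**Chi-squared against exact p.**

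- 1/3 v 0/12. Pearson: 15×(1×12 − 2×0)² / (3×12×1×14) = 2160/504 = 4.29, p = 0.038. Fisher: the single event falls in the cohort of 3 with probability 3/15, p = 0.20. With Yates correction: 15×(12 − 7.5)² / 504 = 0.60, p = 0.44.
- 0/6 v 3/6. Pearson: 12×18² / (6×6×3×9) = 3888/972 = 4.00, p = 0.046. Fisher: 2×C(6,3)/C(12,3) = 40/220 = 0.18. Yates: 12×(18 − 6)²/972 = 1.78, p = 0.18.
- Three cohorts, 2/3, 0/3, 1/12. The pooled rate is 3/18 and the expected events are 0.5, 0.5, 2. Each term is (O − E)²/[E×5/6], giving 5.4 + 0.6 + 0.6 = 6.6 on 2 df, p = exp(−3.3) = 0.037. Freeman-Halton: of C(18,3) = 816 arrangements, 36 + 36 + 9 + 9 + 1 + 1 = 92 are no more probable than the one observed, p = 92/816 = 0.113.

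**True size of the uncorrected test at nominal 5%,** by summing binomial probabilities over all rejecting tables:

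| Cohorts | 10% rate | 33% rate | Maximum over rates 2%–98% |
|---|---|---|---|
| 3 v 3 | 0.15% | 2.2% | 3.1% |
| 3 v 6 | 1.5% | 3.8% | 3.9% |
| 6 v 6 | 1.7% | 6.7% | 6.8% |
| 3 v 12 | 8.7% | 4.4% | 8.8% |
| 6 v 12 | 3.9% | 6.2% | 6.7% |
| 3/3/6 | 2.4% | 6.1% | 7.3% |
| 3/3/12 | 3.2% | 4.9% | 5.6% |
| 3/6/12 | 5.6% | 4.1% | 6.2% |
| 6/6/12 | 4.7% | 5.0% | 5.2% |

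The lowest and highest entries can be checked by hand. For 3 v 3 only 0/3 v 3/3 rejects, so the size at 10% is 2×0.1³×0.9³ = 0.0015. For 3 v 12 the table 1/3 v 0/12 alone contributes 3×0.1×0.9²×0.9¹² = 0.069 of the 0.087.

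**Continuous measures.** Exact Mann-Whitney for 3 v 3 cannot go below 2/C(6,3) = 0.10. At complete separation the uncorrected normal approximation gives 0.0495 against exact 0.10 for 3 v 3, but 0.0094 against 0.0044 for 3 v 12, so the direction of error varies. Three unadjusted pairwise 5% tests give 1 − 0.95³ = 14% family-wise error if independent. They share cohorts, and simulated pairwise t-tests give about 12–13%.

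**The case against.** The strongest reply is that little harm follows. The paragraph is conditional on sample size, the continuous tests are qualified, and no escalation decision uses these p-values. Adverse events and quality of life have their own tables or models. The false-positive rate of the all-cohort test after expansion stays near 5%. Part of the gap to Fisher's p reflects Fisher's conservatism. Chi-squared does accept three cohorts, and if level 2 fails and level 1 becomes the MTD only two cohorts exist, so two-sample tests would fit.

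All of this stands, and it limits the point. It does not remove it: the qualifiers name no threshold and no alternative, the maximum sample is fixed at 24, and the categorical sentence still covers response.

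Three stronger readings are tempting and are not supported.

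- A reader might infer that every named test gives p-values several times too small. That is shown only for uncorrected chi-squared against the conditional exact p. The t-test is not a large-sample approximation, Mann-Whitney has an exact form, and with Yates correction the understatement disappears in the two-cohort examples shown or turns into overstatement.
- A reader might want ordered trend tests required. From cohort 3 onward Section 3.2 admits patients previously treated with venetoclax, so dose order is mixed up with prior exposure and a trend p-value would not isolate dose.
- A reader might extend the criticism to the log-rank tests. Those compare biomarker groups, not dose cohorts, and are already labelled exploratory.

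**Conclusion.** The concern holds for the chi-squared tests between dose cohorts. In plausible tables the uncorrected p-value is about 3 to 5 times smaller than the exact one and falls on the other side of 0.05 (0.20/0.038 = 5.2; 0.18/0.046 = 4.0; 0.113/0.037 = 3.1). The actual size varies from 0.15% to 8.8% with cohort sizes and event rate, so the nominal level means little for any one comparison. The highest value belongs to a pairwise 3 v 12 comparison at event rates near 8% (or 92%). These figures assume a two-sided 5% level, no continuity correction and a common event rate across cohorts.

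The two-sample tests for continuous measures are a separate and smaller mismatch with up to four doses. The effect is confined to secondary analyses, mainly response by dose. The MTD and the escalation rules are untouched.

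**What to change.** In Section 12.6.2:

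1. Report response and other categorical outcomes by dose cohort with exact (Clopper-Pearson) confidence intervals, labelled descriptive. The intervals show the uncertainty directly: for 0/3 the upper 95% limit is 1 − 0.025^(1/3) = 71%, and for 0/12 it is 1 − 0.025^(1/12) = 26%.
2. If tests are kept, replace chi-squared with Fisher's exact test (two cohorts) or the Fisher-Freeman-Halton test (three or more). For continuous measures use exact Kruskal-Wallis, or exact Mann-Whitney if only two cohorts exist. Label all of them exploratory.
3. Replace the references to a treatment effect and to arms with differences between dose cohorts.

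The cost is a wording change; the methods are in standard software. The downside is that exact tests are conservative, so some p-values will be larger. No change is needed to the log-rank tests, and ordered trend tests need not be required.
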